^b The 30-day Safety Follow-up visit should be performed 30 days (± 3 days) following the last dose of study therapy. If the patient starts new anticancer therapy within 30 days of the last dose of study medication, the 30-day Safety Follow-up visit should be performed before the start of new anticancer therapy. Only if the patient is unable to return to the study site, a follow-up phone call can be made by the study site to collect any new safety information that occurred during the Safety Follow-up period.

^c ECG assessment for C1D1, and D1 of C2 and beyond should be conducted pre-dose (up to 30 minutes prior to dosing). ECG should be performed on D1 of every cycle. All ECGs should be performed in triplicate on Day 1 of Cycles 1 to 3 for all patients. After C3D1, ECGs are not required to be performed in triplicate unless clinically indicated.

Abbreviations: AE=adverse event; C=cycle; cfDNA=cell-free DNA; D=day; DLT=dose-limiting toxicity; ECG=electrocardiogram; ECOG=Eastern Cooperative Oncology Group; EOT=end of therapy; ICF=informed consent form; MUGA=multi-gated acquisition scan; PD=progressive disease; PK=pharmacokinetics; QD=once daily; RECIST=Response Evaluation Criteria in Solid Tumors; SAE=serious adverse event; WOCBP=women of childbearing potential

Note: (X) = See notes for details.

Table 2: Schedule of Events for Phase 2 (Part C)

Procedure	Screening Period Within 28 Days prior to first dose	Treatment Period			Follow-up Period		Notes
		Cycle 1 (21 days)		Cycle ≥2 (21 days)	Safety Follow-up ^a	Survival Follow-up	
		Day 1	Day 8 (±1 day)	Day 1 (±3 days)	30 (+3) days after last dose		
EGFR C797S status (pre-screening informed consent)	See Notes						Only if central pre-screening done. Can take place any time prior to screening
Written informed consent (Main study)	X						To be obtained prior to any study related procedures. Can take place any time before Day 1
Review inclusion / exclusion criteria	X						All patients must have documented C797S EGFR mt
Demographics/Medical history	X						Including prior antitumor treatment
Physical examination	X	X		X	X		Within 24 hours prior to dosing. May be symptom directed during treatment period. Examination of skin should be performed at each timepoint.
Ophthalmological examination	X	As clinically indicated			X		See Section 7.1.5
Height and weight	X	X		X	X		Height at screening only
Vital signs	X	X	X	X	X		Heart rate, blood pressure, body temperature

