Hematology	X	X	X	X	X		Assessment prior to first day of dosing may be done up to 72 hours prior to dosing (Section 7.1.4) All other assessments may be done within 48 hours prior to dosing, See Section 7.1
Chemistry	X	X	X	X	X		Assessment prior to first day of dosing may be done up to 72 hours prior to dosing (Section 7.1.4) All other assessments may be done within 48 hours prior to dosing. See Section 7.1

Procedure	Screening Period Within 28 Days prior to first dose	Treatment Period			Follow-up Period		Notes
		Cycle 1 (21 days)		Cycle ≥2 (21 days)	Safety Follow-up ^a	Survival Follow-up	
		Day 1	Day 8 (±1 day)	Day 1 (±3 days)	30 (+3) days after last dose		
Coagulation	X	X		X	X		Assessment prior to first day of dosing may be done up to 72 hours prior to dosing (Section 7.1.4) All other assessments may be done within 48 hours prior to dosing. See Section 7.1
Urinalysis	X	X		X	X		Assessment prior to first day of dosing may be done up to 72 hours prior to dosing (Section 7.1.4) All other assessments may be done within 48 hours prior to dosing. See Section 7.1
Pregnancy test	X	X		X			For WOCBP only: Serum pregnancy test required at screening only. See Section 7.1
Local ECG ^b	X	X		X	X		12-lead ECG. Additional ECG monitoring as clinically indicated. See Section 7.1
Adverse events	X	X			X	(X)	From signing ICF through 30-day safety follow-up. (X) only related SAE Investigator becomes aware of
Concomitant medications	X	X	X	X	X		From signing ICF through 30-day safety follow-up.
ECOG Performance Status	X	X		X	X		
Patient reported outcomes	X			X	X		During treatment period, to be assessed as close as possible to the tumor assessments.
PK sampling		See Table 13					
cfDNA blood samples		X		X	X		From C3D1 onwards, every other cycle. After 12 months, every 3 cycles
Tumor tissue samples	X			(X)	(X)		(X) On-treatment biopsy optional; can be done at one of these timepoints

Procedure	Screening Period Within 28 Days prior to first dose	Treatment Period			Follow-up Period		Notes
		Cycle 1 (21 days)		Cycle ≥2 (21 days)	Safety Follow-up ^a	Survival Follow-up	
		Day 1	Day 8 (±1 day)	Day 1 (±3 days)	30 (+3) days after last dose		
Radiologic tumor assessment	X	X			(X)	(X)	Every 6 weeks (±7 days) from C1D1 irrespective of cycle. After 12 months, every 9 weeks (±7 days). (X) Patients who discontinue study treatment without radiographic PD will continue every 9 weeks (±7 days) until radiographic PD. See Section 7.1

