3.3. Phase 2 – Part C

Objectives	Endpoints
Phase 2	
Primary	

 To assess the efficacy of TAS3351 	
 ORR per RECIST v1.1 by ICR
Secondary	

 To further assess the efficacy of TAS3351 	
 DoR, PFS, and DCR by ICR ORR, DoR, PFS, and DCR by Investigator assessment Intracranial ORR (icORR) and DoR (icDoR) by ICR and Investigator assessment Overall survival (OS)

 To evaluate the safety and tolerability of TAS3351 	
 AEs, including SAEs, clinical laboratory tests, vital signs, and 12-lead ECGs graded according to CTCAE v5.0

 To evaluate patient reported outcomes (PROs) 	
 EORTC QLQ-C30 and EQ-5D-5L
Exploratory	

 To investigate biomarkers of response to TAS3351 and determine their potential association with efficacy 	
 Biomarkers from tumor tissue and blood samples, including (but not limited to) DNA/RNA, protein, and cfDNA analysis

 To explore the potential exposure-response associations for efficacy and safety 	
 Exposures estimated by Population PK model and selected efficacy and safety measures

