4.11. Randomization and Blinding

No blinding of treatment assignments is required as this study is open-label.

No randomization is planned in Part A and Part C, and is only planned in Part B if 2 dose levels of TAS3351 are evaluated in Part B (see Section 4.2.2). Should 2 dose levels be evaluated, a total of 40 patients with C797S *EGFR*mt will be enrolled in Part B and will be randomized at a 1:1 ratio between the two treatment arms (ie, TAS3351 dose levels).

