5.2. Exclusion Criteria

A patient must not meet any of the following exclusion criteria to be eligible for participation in this study:

1. Currently receiving an investigational drug in a clinical trial or participating in any other type of medical research judged not to be scientifically or medically compatible with this study
2. Has received prior treatment with any of the following within the specific time frame prior to the first dose of study treatment:
 - a. Major surgery/surgical therapy for any cause within 4 weeks; the patient must have recovered adequately from the toxicity and/or complications of the intervention prior to starting study treatment
 - b. Chemotherapy, biologic therapy, targeted therapy, immunotherapy, or investigational agents within 5 half-lives or within 4 weeks (whichever is shorter) prior to the first dose of study treatment. Patient must have recovered from toxicities of the prior therapy based on the Investigator's judgement prior to starting study treatment
 - c. No prior treatment with:
 - (i). **Part A1** (Phase 1 Dose Escalation): Systemic immunotherapy (eg, PD-1/PD-L1 antibody)
 - (ii). **Parts A2, B, and C**: Any EGFR C797S mutation-targeting agent (eg, BLU-945)
 - d. Radiotherapy prior to the start of study treatment within:
 - (i). 2 weeks for radiation therapy of non-thoracic regions (7 days for palliative radiation of single lesions)
 - (ii). 3 months for radiation therapy including thoracic region.

Patients must have recovered from all radiation-related toxicities, not require corticosteroids, and not have had radiation pneumonitis.
3. Have any unresolved clinically relevant toxicity of Grade ≥ 2 from previous anti-cancer treatment, except for alopecia, skin pigmentation, and Grade 2 prior platinum-therapy related neuropathy. Patients with chronic, but stable Grade 2 toxicities may be allowed to enroll if the Investigator and Sponsor agree.

4. Any strong and moderate inhibitors/inducers of cytochrome P450 (CYP) 3A two weeks prior to start of therapy. If a patient is receiving strong inhibitors/inducers of CYP3A (see [Appendix A](#)), these medications and substances must be discontinued ≥ 2 weeks prior to the first dose of study treatment.
5. Has the following CNS metastases disease status:

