7.1.6. PRO Measurements

For patients enrolled in Part C, patients' health-related quality of life, symptoms, functioning, and general well-being will be captured using PRO measures and collected according to the Schedule of Events (Section 1.3).

EORTC-QLQ-C30:

The EORTC-QLQ-C30 consists of 30 core items, with the 4-point Likert scales ranging from 1: "Not at all" to 4: "Very much". There are 2 items for global health status/quality of life. Functional scales include physical functioning (5 items), role functioning (2 items), emotional functioning (4 items), cognitive functioning (2 items), and social functioning (2 items). Symptom scales/items include fatigue (3 items), nausea and vomiting (2 items), pain (2 items), dyspnea; insomnia; appetite loss; constipation; diarrhea; and financial impact (1 item each).^{30,31}

EQ-5D-5L:

The EuroQol-5D (EQ-5D) is a standardized measure of the patient's health-related quality of life. The 5-level version of the EQ-5D (EQ-5D-5L) consists of 2 pages: the EQ-5D descriptive system and the EQ visual analogue scale (EQ VAS). The EQ-5D-5L descriptive system comprises the following five dimensions: mobility, self-care, usual activities, pain/discomfort and anxiety/depression. Each dimension has 5 levels: no problems, slight problems, moderate problems, severe problems, and extreme problems. The EQ VAS records the patient's self-rated health on a vertical visual analogue scale where the endpoints are labelled 'The best health you can imagine' and 'The worst health you can imagine'. The VAS can be used as a quantitative measure of health outcome that reflects the patient's own judgement. See <https://euroqol.org/eq-5d-instruments/>.

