9. EFFICACY EVALUATIONS

9.1. Efficacy Criteria

Efficacy parameters will be evaluated by the investigator/local radiologist based on tumor imaging (including CT/MRI) according to RECIST v1.1 guidelines.²⁸ Planned time points for all efficacy assessments are provided in the Schedule of Events ([Table 1](#) and [Table 2](#)).

Primary efficacy evaluation of TAS3351 will be based on independent central review (ICR) for patients enrolled in Part B and C of this study. In addition, efficacy will be assessed by the investigator/local radiologist for all patients.

Determination of disease response for clinical management and discontinuation of study treatment of patients will be assessed at the clinical sites per RECIST v1.1. If the investigator determines that a patient has developed clinical disease progression manifested by symptomatic deterioration but not supported by radiographic evidence of progression, the patient may stop treatment. Symptoms of clinical disease progression must be documented in the patient's source documents and must be reported as AEs. Every effort should be made to document objective radiographic disease progression even after discontinuation of treatment.

For additional guidance, refer to RECIST v1.1 specification for standard anatomical radiological imaging.²⁸

See Section [7.1.1](#) for additional efficacy assessment details.

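### Part C collects its only pre-dose PRO at screening, up to 28 days before first dose, and does not require on-treatment forms to be completed before the scan result is known

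*Protocol*

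**What the plan says.** Protocol Section 3.3 makes the EORTC QLQ-C30 and EQ-5D-5L a secondary endpoint of Part C. Their timing is set in Section 1.3, Table 2:

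- **Pre-dose.** The PRO row is marked in the screening column, headed "Screening Period Within 28 Days prior to first dose". The Cycle 1 Day 1 cell is empty. The ECOG row just above it is marked on Cycle 1 Day 1, as are weight, vital signs, hematology and chemistry.
- **On treatment.** The row is marked at Day 1 of Cycle 2 and later (±3 days, 21-day cycles) and at safety follow-up. The note adds "During treatment period, to be assessed as close as possible to the tumor assessments". Scans are "Every 6 weeks (±7 days) from C1D1 irrespective of cycle", then every 9 weeks after 12 months.
- **Order.** Neither the note nor Section 7.1.6, which only refers back to the schedule, says whether the form comes before the scan, its result or the other visit procedures.

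Three other provisions bear on this. Exclusion criterion 2b bars prior systemic therapy "within 5 half-lives or within 4 weeks (whichever is shorter) prior to the first dose of study treatment". Section 4.11 states "No blinding of treatment assignments is required as this study is open-label". Section 9.1 states "Determination of disease response for clinical management and discontinuation of study treatment of patients will be assessed at the clinical sites per RECIST v1.1", so the site holds a scan reading it can share with the patient.

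Protocol Section 12.7.5 leaves the PRO methods to the SAP. The supplied SAP (Section 1) covers Parts A and B only, so no Part C PRO baseline, change score or analysis is defined.

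**The concern.** Part C has one arm, so a timing problem in the questionnaire cannot cancel between groups. The natural use of a schedule with one pre-dose form and repeated later forms is a within-patient comparison. If the pre-dose form is several weeks old at first dose, that comparison also covers the untreated interval. In that interval the disease may progress, or the patient may recover from the previous drug, since the washout in criterion 2b can fall inside the screening window. A later analysis cannot recover a Day 1 value that was never collected.

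The second issue is what the patient knows when answering. With no order set, a form may be completed after the site has told the patient about response or progression, and the answers may then partly reflect that news.

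What is at stake is how clearly a named secondary endpoint can be read.

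**Working it through.** The documents give no PRO effect size, variability or sample-size figure, so there is no stated figure to reproduce. The check is arithmetic on the schedule windows.

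**Inputs (Table 2).** Days from screening form to first dose, g: 0 to 28. Days on drug at a later form, t: 21 ±3 at Cycle 2 Day 1, and 42 ±7 at the first scan.

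**Formula.** Untreated share of the interval between forms = g / (g + t).

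| Screening form | Later form | Nominal share | Range over the window |
|---|---|---|---|
| Day -28 | Cycle 2 Day 1 | 28/49 = 57.1% | 28/52 = 53.8% to 28/46 = 60.9% |
| Day -28 | First scan | 28/70 = 40.0% | 28/77 = 36.4% to 28/63 = 44.4% |
| Day -14 | Cycle 2 Day 1 | 14/35 = 40.0% | 14/38 = 36.8% to 14/32 = 43.8% |
| Day -14 | First scan | 14/56 = 25.0% | 14/63 = 22.2% to 14/49 = 28.6% |

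The Day -28 rows are ceilings. With a form on Day 1 before dosing, g = 0 and every share is 0%. With a 72-hour pre-dose window, as allowed for the first-dose laboratory tests, the largest shares are 3/(3 + 18) = 14.3% at Cycle 2 Day 1 and 3/(3 + 35) = 7.9% at the first scan.

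**Order of scan and form.** The ±7-day scan window and ±3-day visit window together allow up to 7 + 3 = 10 days between scan and visit, in either order. The result can therefore be known before the form is completed, but need not be.

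**Row against note.** The row marks every Day 1 from Cycle 2, that is every 3 weeks. The note ties the forms to scans at 6 and later 9 weeks. Read literally, the first on-treatment form (about day 21) precedes the first on-treatment scan (about day 42). Read by the note, the first form is at about day 42. This choice decides whether the 57% or the 40% ceiling applies to the first comparison.

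**Scale, on assumptions only.** None of these inputs is in the documents. On a 0 to 100 scale, an assumed steady drift of 0.25 to 2 points per week over 4 weeks shifts a change score by 4 × 0.25 = 1 to 4 × 2 = 8 points, in either direction. With 100 patients and an assumed SD of 20 to 25, the 95% half-width of a mean change is 1.96 × SD/√100 = 3.9 to 4.9 points. The true drift could lie outside this range or be nil.

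**The case against.** The strongest reply is that the plan specifies no PRO analysis for Part C, so there is no change score to be biased. This is correct as a description. It means the analysis consequence is an inference, but the schedule still fixes which data will exist. If the baseline rule in SAP Section 7.1 (the assessment nearest first dose) were carried into Part C, it would select the screening form, because no later pre-dose form is scheduled.

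It is also fair that other provisions limit carry-over. Criteria 2b and 3 require recovery from earlier toxicity, with listed exceptions, and ECOG must be 0 or 1. The baseline scan is taken in screening too, so placing the form beside it is coherent. These points reduce the concern without removing it: recovery is required by the start of treatment, not by the date of the screening form.

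A reader might infer more than the documents support:

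- **That 28 days, or 40%, is typical.** Both are maxima, and the form may be completed at any time in screening. A share of elapsed days is also not a bias in points.
- **That the old baseline flatters TAS3351.** The direction is unknown. Pre-dose decline would count against the drug, and recovery from earlier toxicity would count for it.
- **That forms will normally be completed at the results visit.** The note asks for closeness to the assessment, not to discussion of its result, so completion on scan day satisfies it. Completion after the result is permitted, not expected.
- **That a link between response and quality of life will be inflated.** No objective or planned analysis in Part C links PROs to response.

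**Conclusion.** The point holds as a cheap improvement to a descriptive secondary endpoint. Followed exactly, Table 2 yields a pre-dose PRO that may be up to 28 days old and may fall during washout, with no Day 1 value. Untreated time can make up at most 57% of the nominal interval to Cycle 2 Day 1 and 40% of that to the first scan (60.9% and 44.4% at the earliest edges of the windows). On-treatment forms have no set order relative to the scan result, so some may be completed after the patient knows it.

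This rests on one assumption: that PROs will be read as within-patient change, which is natural in a single-arm part but not stated. Neither the size nor the direction of any bias can be derived from the documents. The primary endpoint, ORR by independent central review, is unaffected.

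**What to change.** 1. In Table 2, collect the EORTC QLQ-C30 and EQ-5D-5L on Cycle 1 Day 1 before dosing, as baseline. A screening form, if kept, serves only as back-up.
2. In the Table 2 note and Section 7.1.6, state that on-treatment forms are completed before scan results are discussed and before other visit procedures.
3. Reconcile the PRO row (every Day 1 from Cycle 2) with its note (6-weekly, later 9-weekly scans), so that one collection frequency is stated.
4. In the Part C SAP, name the Day 1 form as baseline.

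**Cost.** Short edits to Table 2 and Section 7.1.6, plus a baseline definition in a Part C SAP that is needed anyway. The Day 1 visit already exists, so the burden is a slightly longer first visit, or a second pre-dose form per patient if screening is kept.

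**What remains.** Patients still know they are receiving TAS3351, and on-treatment drift cannot be separated from drug effect without a control arm. PRO results should still be reported as descriptive.

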Table 10:	Recommendations for Managing Non-Hematologic Toxicities	59
Table 11:	Description of TAS3351	65
Table 12:	Study Assessments	66
Table 13:	Schedule for PK and ECG Sampling (QD Dosing)	72
Table 14:	Schedule for PK and ECG Sampling (BID Dosing)	73
Table 15:	Efficacy Endpoint Definitions.....	76
Table 16:	ORR 95%CI for Sample Size of 100 Patients.....	87
Table 17:	Definitions of Analysis Populations.....	87

LIST OF ABBREVIATIONS AND DEFINITIONS OF TERMS

Abbreviation	Definition
AE	Adverse event
AESI	Adverse event of special interest
ALP	Alkaline phosphatase
ALT	Alanine aminotransferase
ANC	Absolute neutrophil count
APTT	Activated partial thromboplastin time
ASCO	American Society of Clinical Oncology
AST	Aspartate aminotransferase
AUC	Area under the plasma concentration-time curve
AUC ₀₋₂₄	Area under the plasma concentration-time curve from 0 to 24 hours
AUC _{inf}	Area under the plasma concentration-time curve to infinity
AUC _{last}	Area under the plasma concentration-time curve up to the last observable concentration
BCRP	Breast cancer resistance protein
BID	Twice daily (or 2 times a day)
BOIN	Bayesian optimal interval design
BUN	Blood urea nitrogen
cfDNA	Circulating free DNA
CHF	Congestive Heart Failure
CI	Confidence interval
CLIA	Clinical laboratory improvement amendments
CL/F	Apparent clearance of drug from plasma after extravascular administration
C _{max}	Maximum plasma concentration
CNS	Central nervous system
CONSORT	Consolidated Standards of Reporting Trials
CR	Complete response
CrCl	Creatinine clearance
CRP	C reactive protein
CSR	Clinical study report
CT	Computed tomography
CTCAE	Common Terminology Criteria for Adverse Events
CYP	Cytochrome P450
DCR	Disease control response
DLT	Dose-limiting toxicity
DMC	Data monitoring committee
DNA	Deoxyribonucleic acid

Abbreviation	Definition
DoR	Duration of response
DRESS	drug rash with eosinophilia and systemic symptoms
EC ₅₀	50% effective concentration
ECG	Electrocardiogram
ECHO	Echocardiography
ECOG	Eastern Cooperative Oncology Group
eCRF	Electronic case report form
EGFR	Epidermal growth factor receptor
EGFRmt	Epidermal growth factor receptor mutation
eGFR	Estimated glomerular filtration rate
E _{max}	Maximum induction ratio
EORTC	European Organization for Research and Treatment of Cancer
FIH	First-in-human
GCP	Good Clinical Practice
G-CSF	Granulocyte colony-stimulating factor
HBs	Hepatitis B surface
HBV	Hepatitis B virus
HCV	Hepatitis C virus
HED	Human equivalent dose
hERG	Human ether-a-go-go related gene
HIV	Human immunodeficiency virus
HNSTD	highest non-severely toxic dose
HRCT	High-resolution computed tomography
HSA	Human serum albumin
IC ₅₀	Half maximal inhibitory concentration
icDOR	Intracranial duration response
ICF	Informed consent form
ICH	International Council for Harmonisation of Technical Requirements for Pharmaceuticals for Human Use
icORR	Intracranial overall response rate
ICR	Independent central review
IEC	Independent ethics committee
ILD	Interstitial lung disease
IRB	Institutional review board
IXRS	Interactive voice/web response system
K _{p, brain}	Brain to plasma concentration ratio
K _{inact}	Inactivation rate constant

Abbreviation	Definition
LVEF	Left ventricular ejection fraction
MedDRA	Medical Dictionary for Regulatory Activities
MRI	Magnetic resonance imaging
MRT	Mean residence time
MTD	Maximum tolerated dose
MUGA	Multi-gated acquisition scan
NSCLC	Non-small cell lung cancer
ORR	Overall response rate
OS	Overall survival
PD	Progressive disease
PFS	Progressive free survival
P-gp	P-glycoprotein
PGx	Pharmacogenomics
PK	Pharmacokinetics
PO	Oral
PRO	Patient reported outcomes
PT-INR	Prothrombin time - international normalized ratio
QD	Once daily
QTc	QT interval corrected
QTcF	QT interval corrected for heart rate using Fridericia's formula
RBC	Red blood cell
RECIST	Response Evaluation Criteria in Solid Tumors
RP2D	Recommended Phase 2 dose
SAE	Serious adverse event
SAP	Statistical analysis plan
SD	Stable disease
SOC	Standard of care
SOP	Standard operating procedure
SPE	Sun protection factor
STD10	Severely toxic dose in 10%
SUSAR	Suspected unexpected serious adverse reaction
T _{1/2}	Terminal elimination half-life
TEAE	Treatment-emergent adverse event
TKI	Tyrosine-kinase inhibitor
t _{max}	Time to maximum plasma concentration
ULN	Upper limit of normal
US or USA	United States or United States of America

Abbreviation	Definition
V _z /F	Apparent volume of distribution during the terminal (λ_z) phase
WBC	White blood cell
WOCBP	Women of childbearing potential

